14 REFERENCES10

1 Background and introduction

Total hip arthroplasty (THA) is an effective treatment for many hip joint diseases, able to improve patients' functional level and quality of life and to make the return to the activities of daily living possible [1] [2]. The improvement in surgical techniques had made the bilateral THA surgery possible, through one-stage procedure [3]. It seems not to be linked to increased in mortality rate or postoperative complications respect to the same two-stage procedure. [4] [5] [6].

The goal of the surgery is not only the pain relief, but also the functional recovery, which could take place through adaptive mechanisms of the non-afflicted limb. Simultaneous bilateral THA surgery doesn't allow these adaptive mechanisms and our clinical observation suggests that in this condition, the recovery of the operated limb could be faster. This is not a new hypothesis, in fact the use of the residual motor potential when adaptive strategies are not possible, has been largely demonstrated in the functional recovery of stroke patients [7]. In this case, the application of movement restrictions to the non-affected body segments and the intensive use of the affected side, promotes the motor and functional recovery [8]. Some authors suggest to apply similar approaches in other pathological conditions [9] [10].

2 Rationale of the study

Actually there are no studies investigating the motor and functional recovery of unilateral THA patients compared to simultaneous bilateral THA patients. Our clinical observation induce to speculate that simultaneous THA patients could achieve better functional and motor recovery of affected limbs caused by the impossibility to develop adaptive mechanisms with the contralateral side.

3 Object of the study

3.1 General objectives

The aim of the study is to evaluate the lower limbs motor and functional recovery in subjects who undergone to unilateral o simultaneous bilateral THA.

3.2 End-points

3.2.1 Primary endpoints

The primary endpoint the evaluation of postural stability and the weight distribution during a stabilometric task performed in "open eyes" and "closed eyes" conditions, and during a "voluntary swing" condition. The postural stability and weight distribution will be evaluated through two force platforms (P-6000 BTS SpA). The platforms will calculate the weight distribution between the two lower limbs and the antero-posterior and mid-lateral displacement of the Centre of Pressure (CoP) applied on the ground. An optoelectronic system with passive markers composed of six infrared cameras (Smart DX, BTS SpA) and 4-channel surface electromyography (FREEEEMG 1000, BTS SpA) will also be used. The markers will be placed on anatomic bony landmark according to the Davis model in order to reconstruct the pelvis, hip, knee and ankle kinematic on the sagittal plane during the stabilometric task [11]. The surface electromyography will be placed on the anterior tibialis and gastrocnemius medialis of both limbs, according to SENIAM recommendation in order to evaluate the muscles activations normalized respect to the maximum voluntary contraction (MVC), the timing of muscle activation respect to the movements of the tibiotarsic joint during the "voluntary swing" and the frequency of activation during the three trials [12].

3.2.2 Secondary endpoints

The secondary endpoint is the spatio-temporal parameters, the kinematic and dynamic profiles and the muscular activities evaluation during the gait. The analysis will be done through the same technologies described before. The force platforms (P-6000 BTS, SpA) will allow to calculate the ground reaction force. The optoelectronic system (Smart DX, BTS SpA) with the passive markers placed on the skin according to the Davis model will be used to estimate the spatio-temporal parameters and the pelvis, hip, knee and ankle kinematic during the step cycle. The eight-channel surface electromyography (FREEEMG 1000, BTS SpA) will be adopted to calculate muscle activation timing during the gait. The probes will be placed on the anterior tibialis, gastrocnemius medialis, rectus femoris, gluteus medius, according to SENIAM recommendations [14]. The ability of the subject to maintain the limb in isometric flexion and abduction position with the knee extended for 10 seconds will also be evaluated. The evaluation of walking ability will be performed through Time Up and Go Test (TUG). At the end of each task, the perception of pain will be investigated through the Numeric Rating Scale (NRS).

4 Patient selection criteria

4.1 Inclusion criteria

- Age between 40 and 65 years old.
- THA surgery for primary or secondary arthrosis.
- THA surgery for primary osteonecrosis.
- Walking ability for at least 50 m without aids.

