4.2 Exclusion criteria

- THA surgery for severe dysplasia (Crowe III e IV).
- THA surgery for ankylosis, sub-ankylosis or surgical fusion of the hip joint.
- THA surgery for a traumatic event.
- THA surgery after previous femoral and / or pelvic osteotomy
- Partial or total THA revision
- Concomitant presence of neurological or musculoskeletal disorders that could affect motor and functional recovery.

5 Study design

The study is a prospective observational study.

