5.1 General Design

Unilateral THA and simultaneous bilateral THA patients will be recruited. They will be evaluated through three stabilometric tests, gait analysis, two strength tests, TUG and pain (NRS). The session trials will be done the day before surgery, seven and forty day after surgery. The stabilometric tasks, the two strength tests and the NRS will be performed also after three days. The stabilometric test will be characterized by "open eyes", "closed eyes" and "oscillations" conditions. The first two stabilometric tests ("open eyes" and "closed eyes") will last 45 seconds and will be repeated three times. Patients will be asked to keep the erected station with the parallel feet placed at an intermalleolar distance of 5 cm. Their arms should be relaxed along their sides. The patient has to maintain the balance looking at a point in front of him placed at 2 meters of distance in "open

eyes" condition. During the "oscillation" task, the subject, will be asked to perform three oscillations on the platforms, one after 10 seconds from each other. The gait analysis will consist of 4 trials in which the subject will be asked to walk on the gaitwalk. During the evaluation session all subjects will wear their underwear and the performance will be recorded through two cameras (eVixta, BTS SpA) in order to check the correct performance. Before the stabilometric tests and gait analysis, the two strength tests will be performed. In the first case patients will be asked to lie in supine position, to keep the hip with the knee completely extended up to 45 ° for 10 seconds. In the second case patients will be asked to lie on his side, to keep the hip abduction with extended knee for 10 seconds. Strength tests will be repeated for the two lower limbs both. The TUG before gait analysis, will consist of standing up from a chair, walking for 3 meters, to turning a cone and to sitting again, the operator will assess the time of the test. The TUG will be repeated for three times after a break of 1 minute and only the best performance will be considered. At the end of each single test the subject will be asked to quantify pain perceived through the NRS scale. This instrument consists of a visual 10 cm line, numbered from 0 to 10, where 0 corresponds to "no pain" and 10 to "maximum pain imaginable". All the tests listed will be performed by a single operator.

6 Statistical consideration

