6.1 Sample size

This protocol refers to a pilot study and therefore there aren't normative data. In literature we found studies evaluating the postural stability in THA patients, which enrolled 20 subjects [13]. For the following protocol, 30 subjects for each group will be considered in order to estimate the change of these parameters between-groups.

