6.2 Analysis

The statistical analysis will be performed at the end of the study through SPSS 20.0. Categorical variables will be described in terms of proportion, while the continuous variables will be described in terms of mean and standard deviation or median and interquartile ranges. Outcomes measures will be checked for normality through Kolmogorov-Smirnov test. T-Student test will be used to confirm the homogeneity of the demographic and continuous variables before surgery for stabilometric task (weight distribution between the two lower limbs, mid-lateral and anterior-posterior displacement of the CoP, pelvis, hip, knee and ankle kinematic, muscular activation normalized by MVC, timing of the muscle activation respect to the movements of the tibiotarsic joint and activation frequency) , during gait analysis (ground reaction force, spatio temporal parameters, pelvis, hip, knee, ankle kinematic and timing of muscles activation), during the segmental strength test (time of the support of the lower limbs in the position decided by the operator), related to the TUG (execution time of the trial) and to the NRS scale (value from 0 to 10). The inter-group and intra-group differences after will be evaluated by ANOVA test for repeated measurements and then an eventual post hoc analysis will be conducted. The statistical significance value will be set at $\alpha=0.05$.

7 Withdrawal of subjects

The patients that for any reason will decide to, they will be immediately excluded from it. The incompleting acquisitions will be excluded from the analysis.

8 Forms and procedures for collecting data and data managing

An Excel file (Attachment B) will be filled in with demographic variables and outcome measures. It will be secured by a password. Only two investigators will collect the data in order to reduce errors.

9 Ethical consideration

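### One whole-patient walking threshold for groups with one or two operated hips may leave severity per operated hip unequal, in an unknown direction, and the unadjusted ANOVA does not deal with it

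*Protocol*

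**What the plan says.** - **Eligibility (Protocol 4.1).** The only functional entry test is "Walking ability for at least 50 m without aids". It applies to the patient as a whole and is the same for both groups. No criterion concerns the severity of an individual hip, although section 4.2 excludes some severe conditions (ankylosis, sub-ankylosis, fusion, Crowe III and IV dysplasia).
- **Design (Protocol 5 and 5.1).** "The study is a prospective observational study"; "Unilateral THA and simultaneous bilateral THA patients will be recruited". There is no randomisation or matching.
- **Hypothesis (Protocol 2).** The investigators expect that "simultaneous THA patients could achieve better functional and motor recovery of affected limbs", so the question is framed per limb.
- **Size and target (Protocol 6.1).** "30 subjects for each group will be considered in order to estimate the change of these parameters between-groups". The number rests on precedent: "This protocol refers to a pilot study and therefore there aren't normative data".
- **Analysis (Protocol 6.2, repeated in the SAP).** "T-Student test will be used to confirm the homogeneity of the demographic and continuous variables before surgery", followed by repeated-measures ANOVA. No covariate is named. The plan does not say what follows if a baseline difference appears, or how two operated limbs in one patient are handled.
- **Data file (Protocol 8).** Attachment B "will be filled in with demographic variables and outcome measures". The attachment is not among the documents, so its exact columns are unknown.

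**The concern.** Unaided walking can depend on both hips. A unilateral candidate with one badly affected hip may pass 50 m by relying on the sound side; a bilateral candidate has no sound side. The protocol's rationale rests on a related idea, that unilateral patients can compensate with the other limb. Applying that idea to pre-operative walking is an inference, but a reasonable one. The same threshold may then admit different ranges of per-hip severity in the two groups.

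If severity before surgery is related to limb function afterwards, part of any difference in operated-limb recovery could come from who was admitted rather than from blocked compensation. The plan's only safeguard is a set of significance tests at baseline.

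**Working it through.** **1. Can the baseline t-test confirm homogeneity?** Inputs: n = 30 per group (Protocol 6.1) and alpha = 0.05 (Protocol 6.2; two-sided assumed, as sidedness is not stated). The documents give no effect size, SD or power, so there is no calculation of theirs to reproduce.

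Noncentrality = d / √(2/30), with 58 degrees of freedom and critical t = 2.00.

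| True baseline gap d (SD) | Noncentrality | Power |
|---|---|---|
| 0.3 | 1.16 | 21% |
| 0.5 | 1.94 | 48% |
| 0.8 | 3.10 | 86% |

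A true gap of half an SD is missed about as often as it is found. The 95% confidence interval for the difference extends about 2.00 × √(2/30) = 0.52 SD either side, so even an observed difference of zero leaves gaps up to about half an SD open.

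**2. How large a gap might the criterion create?** The documents give no per-hip severity, no pass rate and no account of how two hips combine to limit walking. Everything in this step is assumption.

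Model A, 1,000,000 candidates per setting:
- diseased hip N(2, 1) and sound hip N(0, 0.5);
- correlation between two diseased hips 0.3 or 0.7;
- limitation = worse hip + w × other hip + N(0, 1);
- eligible if limitation is below 3, 4 or 5.

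Results are the mean severity of accepted operated hips, bilateral minus unilateral, in SD units. Negative means bilateral hips are milder.

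| w | Candidate pools equal | Bilateral candidates start 0.5 SD worse per hip |
|---|---|---|
| 0.25 | −0.19 to −0.05 | +0.13 to +0.38 |
| 0.5 | −0.35 to −0.12 | −0.08 to +0.26 |
| 1 | −0.63 to −0.30 | −0.42 to −0.01 |

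With w = 0 (the worse hip alone governs walking) and equal pools, the gap stays within about 0.03 SD of zero.

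Model B uses different assumptions: operated hip N(0, 1), healthy hip mean −2, noise SD 0.5, between-hip correlation 0 to 0.8, and 50% to 90% of unilateral candidates passing. With equal pools, in pooled-SD units:
- sum of both hips: −1.14 to −0.58;
- worse hip + 0.3 × better hip: −0.51 to −0.18;
- worse hip only: −0.10 to +0.11.

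Both models agree that the gap ranges from none to substantial, and that its sign depends on the combination rule and the candidate pools.

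**3. Which way would a gap push the result?** Suppose bilateral hips are milder by g = 0.5 SD, surgery type has no effect, SDs are equal before and after, and the pre-post correlation is r. The post-operative level then differs by r × g in favour of bilateral. The change from baseline differs by (1 − r) × g against bilateral, because milder hips have less to gain. Noncentrality is r·g / √(2/30) for level and [(1 − r)·g / √(2(1 − r))] / √(2/30) for change.

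| r | Level bias (SD, toward hypothesis) | P(significant), level | Change bias (SD, against hypothesis) | P(significant against), change |
|---|---|---|---|---|
| 0.3 | 0.15 | 9% | 0.35 | 20% |
| 0.5 | 0.25 | 16% | 0.25 | 16% |
| 0.7 | 0.35 | 27% | 0.15 | 11% |

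The nominal rate is 5% for the two-sided level test and 2.5% in one direction for the change column. Section 6.1 names change as the target; section 6.2 does not say whether the group effect or the group-by-time interaction carries the conclusion.

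**4. Which outcomes are exposed?** CoP displacement and load distribution (Protocol 3.2.1) are whole-body or between-limb quantities. The mechanism bears mainly on limb-level measures: hip, knee and ankle kinematics, EMG and hold time. Some of these also sit within the primary endpoint.

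**The case against.** The strongest objection is that the selection effect is modelled, not shown. This stands. Setting w to zero removes it, and letting bilateral candidates start somewhat worse mostly reverses it for w of 0.25 and 0.5. The exclusions in section 4.2 also remove some of the severe hips a unilateral candidate might otherwise carry past the threshold.

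A reader might infer that the criterion tilts the comparison toward the investigators' hypothesis. The documents do not support that. It needs a particular rule for combining hips, similar candidate pools, and a comparison of post-operative levels; on change from baseline the same gap works the other way.

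A reader might also infer that the baseline check is blind to the problem. That goes too far. The listed t-tests include hip kinematics and hold time, and section 5.1 has the strength tests done on both limbs. The weakness is power, not absence of limb-level data. Nor can per-hip columns be called missing from Attachment B, which is not available.

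Finally, this is a pilot, and unequal severity is a general hazard of non-randomised groups. That limits the weight of the point, but not the case for adjusting with data already collected.

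**Conclusion.** The concern holds in a limited form. A single whole-patient threshold is applied to non-randomised groups with one or two operated hips, so severity per operated hip may differ between those accepted. The size and direction of any bias are unknown: they depend on how the hips combine to limit walking, on the candidate pools, and on whether level or change is compared. The illustrative gaps rest wholly on the stated assumptions.

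What does not depend on the selection models is that 30 per group gives the t-test 21% and 48% power for gaps of 0.3 and 0.5 SD (two-sided alpha 0.05 assumed). A non-significant result therefore cannot confirm homogeneity, and the planned ANOVA names no adjustment. The consequence falls mainly on limb-level outcomes and leaves CoP displacement and load distribution largely untouched.

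**What to change.** Keep the 50 m criterion and change the analysis and reporting:

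1. In between-group analyses of operated-limb outcomes, use the post-operative visits as outcomes and include the operated limb's own pre-operative measure as a covariate, for example hip range in gait or hold time from the day before surgery. Hip range is preferable if many patients reach the full 10 seconds of the hold test before surgery. Add radiographic grade where the surgical work-up already contains it. With the outcome's own baseline in the model, level and change give the same adjusted group difference, so the sign conflict in step 3 no longer arises.
2. Allow for two operated limbs in one patient, by a patient-level random effect or by averaging the two limbs. Otherwise 30 bilateral patients count as 60 independent limbs.
3. Report baseline differences per operated hip with 95% confidence intervals, and do not treat non-significant t-tests as evidence of comparability.
4. Log and report, by group, how many surgical candidates failed the 50 m rule. This cannot be reliably reconstructed later.

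The cost is some chart abstraction, one or two model terms and a screening count. The adjustment reduces selection bias but cannot fully remove it, because a single pre-operative measure captures severity imperfectly.

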4.2 Exclusion criteria

- THA surgery for severe dysplasia (Crowe III e IV).
- THA surgery for ankylosis, sub-ankylosis or surgical fusion of the hip joint.
- THA surgery for a traumatic event.
- THA surgery after previous femoral and / or pelvic osteotomy
- Partial or total THA revision
- Concomitant presence of neurological or musculoskeletal disorders that could affect motor and functional recovery.

5 Study design

The study is a prospective observational study.

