OFFICIAL TITLE: Functional recovery after monolateral or bilateral total hip arthroplasty

PROTOCOL IDENTIFYING NUMBER: CLF17/02

DATE: 14/12/2017

Statistical analysis plan

The statistical analysis will be performed at the end of the study through SPSS 20.0. Categorical variables will be described in terms of proportion, while the continuous variables will be described in terms of mean and standard deviation or median and interquartile ranges. Outcomes measures will be checked for normality through Kolmogorov-Smirnov test. T-Student test will be used to confirm the homogeneity of the demographic and continuous variables before surgery for stabilometric task (weight distribution between the two lower limbs, mid-lateral and anterior-posterior displacement of the CoP, pelvis, hip, knee and ankle kinematic, muscular activation normalized by MVC, timing of the muscle activation respect to the movements of the tibiotarsic joint and activation frequency) , during gait analysis (ground reaction force, spatio temporal parameters, pelvis, hip, knee, ankle kinematic and timing of muscles activation), during the segmental strength test (time of the support of the lower limbs in the position decided by the operator), related to the TUG (execution time of the trial) and to the NRS scale (value from 0 to 10).

The inter-group and intra-group differences after will be evaluated by ANOVA test for repeated measurements and then an eventual post hoc analysis will be conducted. The statistical significance value will be set at $\text{Alpha}=0.05$.

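### Must the plan spell out how a replaced or diseased opposite hip is handled in the unilateral group?

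*Protocol*

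**What the plan says.** The groups are defined by operation. Protocol Section 5.1 states "Unilateral THA and simultaneous bilateral THA patients will be recruited", and the aim in Section 3.1 compares recovery between patients having one or the other procedure.

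The hip-specific criteria in Sections 4.1 and 4.2 describe the planned operation. The entry closest to earlier surgery is the exclusion "Partial or total THA revision". A general exclusion covers "Concomitant presence of neurological or musculoskeletal disorders that could affect motor and functional recovery". Candidates must also be able to walk 50 m unaided.

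The rationale gives the other leg a role. Section 1 says of functional recovery "which could take place through adaptive mechanisms of the non-afflicted limb", and Section 2 suggests that bilateral patients may do better, "caused by the impossibility to develop adaptive mechanisms with the contralateral side". Within the primary endpoint (Section 3.2.1), "The platforms will calculate the weight distribution between the two lower limbs".

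On analysis, Section 6.2 and the SAP share one text: "T-Student test will be used to confirm the homogeneity of the demographic and continuous variables before surgery", followed by repeated-measures ANOVA with post hoc tests. No covariate, stratum, subgroup or sensitivity analysis is named. On data capture, Section 8 says "An Excel file (Attachment B) will be filled in with demographic variables and outcome measures". Attachment B is not among the documents.

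**The concern.** The suggested mechanism needs a usable opposite leg in unilateral patients, yet no criterion names one. Someone with a recovered primary replacement on the other side is not caught by the revision exclusion, and by procedure is having a unilateral operation. The musculoskeletal exclusion names no side, joint or group. In bilateral patients the second hip is diseased by definition, so a literal reading seems to need an unwritten exception.

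If unilateral patients with a poor opposite hip entered and compensated less, the group contrast would shrink, most directly in weight distribution. Without randomisation, nothing balances this factor. As an illustration, take a two-group comparison that has 80% power. If 10%, 20% or 30% of the unilateral group showed no contrast at all, power would fall to 71%, 61% or 50%.

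**Working it through.** **Step 1. Which patients are in doubt?** Setting the criteria beside the rationale gives these cases.

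- *Opposite hip limits recovery, whether arthritic or replaced.* The general exclusion turns on whether a disorder could affect motor and functional recovery. That is the property at issue, so the clause plausibly applies. The 50 m walking criterion also limits severe disease.
- *Opposite hip abnormal but not limiting.* The patient may enter. If the leg can still compensate, the contrast in Section 2 is intact.
- *Recovered primary replacement on the opposite side.* The text does not settle this. Section 1 distinguishes one-stage from two-stage bilateral surgery, so the patient can be read as a two-stage bilateral case belonging to neither group. If enrolled as unilateral with a well-functioning prosthetic leg, there may be no loss.
- *Second hip in the bilateral group.* Concomitant most naturally means in addition to the condition being operated on. Section 4.1 lists arthrosis and osteonecrosis as indications, so a sensible screener would not exclude bilateral patients for the hips being replaced.

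What remains is borderline judgement at screening.

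**Step 2. Can the documents size the harm?** No. Section 6.1 gives 30 per group for a pilot, with no effect size, SD or power, so there is no planned figure to reproduce. Any magnitude needs three assumptions: the effect, the share p of unilateral patients affected, and the fraction L of the contrast lost in them.

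**Step 3. Would a sensitivity analysis settle it?** Assume the effect d that 30 per group detects with 80% power at two-sided 0.05. The normal approximation gives (1.960 + 0.842) × √(2/30) = 0.723 SD; the noncentral t gives 0.736 SD, used here.

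- Expected contrast, all patients: d(1 − pL).
- Expected contrast, sound-hip patients only: d.
- Expected shift between the two: d × p × L.
- The restricted set is nested in the full set and the bilateral mean cancels. With m sound-hip patients out of 30, the 95% sampling noise of the shift is therefore 1.96 × √(1/m − 1/30) SD.

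For p = 10%, m = 27: shift 0.736 × 0.10 = 0.07; noise 1.96 × √(1/27 − 1/30) = 0.12.

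| Assumed p | m | Shift, L = 1 (SD) | Shift, L = 0.5 (SD) | 95% noise (SD) |
|---|---|---|---|---|
| 10% | 27 | 0.07 | 0.04 | 0.12 |
| 20% | 24 | 0.15 | 0.07 | 0.18 |
| 30% | 21 | 0.22 | 0.11 | 0.23 |

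Even with the contrast wholly lost, each expected shift lies inside the noise. At half loss it is at most about half the noise. These figures use a two-sample comparison, while the plan is repeated-measures ANOVA, so they show the order of size only.

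**The case for a change.** The best case for a change is that this is no routine request for another covariate. The hypothesis turns on the opposite leg, the primary endpoint measures load sharing between the legs, and the remedy looks cheap: one baseline item, one clarifying sentence and one sensitivity analysis. Pre-surgery weight distribution and strength tests on both legs describe function, but not surgical history or diagnosis, and are used before surgery only to check that the groups are alike. A pilot, on this view, should record what its hypothesis depends on.

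Some of this stands. The criteria do not name an earlier opposite-side replacement, two screeners could differ on a borderline hip, and the analysis text makes no use of the item.

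The step from there to a needed change does not stand. The loss of power quoted under the concern rests wholly on assumed values. Whether the item is already collected cannot be known without Attachment B. The analysis is also less cheap than it looks: Section 3.2.1 lists weight distribution, centre-of-pressure displacement, kinematics and muscle activity over three conditions, so one sensitivity analysis becomes many tests at 0.05. The alternative, excluding such patients outright, would give the two groups different eligibility rules in a non-randomised comparison and narrow the unilateral population.

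**Conclusion.** No change follows. This is an ambiguity in eligibility wording that investigators can resolve sensibly with the functional exclusion already in Section 4.2. It is not evidence that such patients would enrol, and no stated rule or figure is shown to give a wrong result. The comparison by procedure in Section 3.1 tolerates a mixed unilateral group; only the mechanism offered as speculation in Section 2 is touched.

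The size is unknown and could be nil. The proposed sensitivity analysis would not reliably show which case applies: expected shifts of 0.07 to 0.22 SD, at assumed shares of 10% to 30% and total loss, stay below noise of 0.12 to 0.23 SD. That rests on an effect of 0.736 SD back-calculated from 30 per group. A sentence on the opposite hip, or a descriptive baseline item if Attachment B lacks one, would be harmless tidying that the planned analysis does not depend on.
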